## SUMMARY

**Rationale:** Initial clinical studies have shown that stimulation of the dorsal root ganglion (DRG) can significantly reduce chronic intractable pain. These results have supported the CE marking of the Spinal Modulation Neurostimulator system in the management of chronic pain. As DRG stimulation with the Axium® Neurostimulator System is a new type of Spinal Cord Stimulation (SCS) and to follow the requirements of the AIMDD, Spinal Modulation would like to collect clinical data on this commercially available therapy.

**Objective:** The purpose of this PRospEctive post market trial of Drg stlimulation ("PREDICT") is to evaluate the commercially available Axium® Neurostimulator System in the management of intractable chronic pain in patients that are routinely scheduled to receive a Spinal Modulation Axium® Neurostimulator System.

- Primary Objective: Evaluate reduction in pain (VAS)
- Secondary Objectives: Safety (AE/SAE), Quality of life, Physical functioning, Subject satisfaction and Device performance

**Study design:** This is a prospective, post market, multi centre, single-arm trial.

**Device:** Commercially available, CE marked, Axium® Neurostimulator System for the management of chronic intractable pain (CE 567069).

**Study population:** Up to 125 Males and females at least 18 years of age suffering from chronic neuropathic pain for at least 6 months that are routinely scheduled to receive a commercially available Axium® Neurostimulator System.

**Intervention:** Under monitored anaesthesia care, subjects will undergo minimally invasive placement of leads in the lateral epidural space of the neural foramen following standard clinical procedures. Subjects having successful trial stimulation will receive the fully-implantable system and will be followed for 24 months. They will be asked to complete several questionnaires at baseline and at follow-up visits.

**Follow-up visits:** The patients will visit the hospital for the following visits: Baseline, Trial NeuroStimulator (TNS) procedure, End of TNS (if applicable), Implantable NeuroStimulator (INS) procedure, 1 week follow-up (FU), 4 week FU, 3 month FU, 6 month FU, 12 month FU and 24 month FU. If needed the site can contact the patients by phone at 8 weeks FU, 9 months FU, and 18 months FU.

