## 2. OBJECTIVES

The objective for this prospective, multi centre DRG stimulation trial is to assess the performance of the commercially available CE marked Axium® Neurostimulator System in the management of chronic intractable pain.

Primary objectives:

1. Pain relief measured using a Visual Analogue Scale (VAS). The average pain reduction experienced as well as the percentage of subjects with at least a 50% pain reduction will be evaluated.

Secondary Objectives:

[figure not shown]

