### 7.3 Study procedures

1.15 Study procedures  
During the prospective trial, data will be collected on Case Report Forms (CRFs). A copy of the CRFs will be provided for review.

*Subject Screening and baseline*

Subjects presenting with chronic pain for at least 6 months will be screened for possible entry into the prospective trial. Subjects will be screened according to the Inclusion/Exclusion criteria and only subjects meeting all Inclusion criteria and none of the Exclusion criteria will be enrolled. The prospective trial will be explained to all subjects and subjects will provide informed consent with an REC-approved Informed Consent Form prior to any data collection. Subjects will be allowed to discuss their participation in the trial with the study physician, clinical staff, family, friends and personal or external physician.

Following subject screening and acquisition of Informed Consent, subjects will undergo a baseline assessment to collect clinical data prior to lead implantation and stimulation. Baseline pain scores (VAS) will be evaluated using the average score from a 4 day pain diary completed by subjects before their trial procedure. Women of child bearing potential will take an HCG-based pregnancy test to confirm that they are not pregnant prior to entry into the trial.

*Trial Stimulation Lead Implant Procedure*

Following collection of baseline measurements, subjects will begin Phase 1 of the two-step treatment process. Phase 1 is the Trial Phase and consists of percutaneously implanting quadrapolar neurostimulator leads into the epidural space. The techniques used in implanting the Spinal Modulation Neurostimulator System are consistent with standard of care practices used by other approved spinal cord stimulator systems. The *Physician Implant Manual* provides a detailed description of the implant and surgical technique. Perioperative programming will be performed to verify proper lead placement.

*End of Trial Phase*

At the end of the Trial Phase, pain relief will be assessed to determine whether a subject should receive an INS implant. This may be done in the theatre during the TNS procedure or after an extended trial period of no more than 30 days based upon the type of pain, the location of the pain, and the standard procedures at the hospital.

*INS Implant Procedure*

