Eligible subjects willing to continue with the implant will undergo surgery to insert the fully implantable neurostimulator (INS). If the epidural leads were removed during the trial period, new leads will also be implanted at this time (see *Physician Implant Manual* for detailed information regarding the procedure). Each subject will receive a hand-held Patient Programmer that can be used to adjust stimulation amplitude as needed throughout the study duration.

Post-implant programming to adjust stimulation settings will occur either immediately after the surgery or the day following implantation.

*Regular Follow-ups*

Subjects will be followed according to the follow-up schedule for 24-months following implant at regular intervals according to standard clinical practice: 1-week ( $\pm 5$  days), 4 weeks ( $\pm 1$  week), 3 month ( $\pm 2$  weeks), 6 month ( $\pm 2$  weeks), 12 months ( $\pm 2$  weeks) and 24 months ( $\pm 2$  weeks). The given time-windows are advisable and therefore visits outside the time windows will not be seen as a protocol deviation. If desired, the Investigators may call the subjects for evaluation at 8-weeks, 9-months and 18 months post-implant.

Prior to completing the required assessments, the subject will have his/her stimulator reprogrammed if needed.

*24-month follow-up (Study Exit)*

The study will end 24 months following INS implantation. At this visit, the regular follow-up assessments as outlined in appendix A will be acquired and a trial exit form will be completed. Following completion of the study, subjects will continue to use the Axium® Neurostimulator System. They will be monitored by their physician as needed in accordance with standard clinical practice.

*Interim Programming/Revision/Replacement/Explant (if necessary)*

During the course of the trial, subjects will have the option to return to the study site at any time to have their neurostimulator re-programmed to achieve maximal benefit. If any part of the Axium® Neurostimulator System becomes dysfunctional or requires adjustment following implantation, it is up to the investigator to perform an interim visit. In appendix A, the assessments are listed for an interim visit and a revision (if applicable).

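### Section 7.3 puts any reprogramming before the follow-up assessments and does not visibly exempt the primary VAS, so scores may reflect settings changed at that same visit

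*Protocol*

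**What the plan says.** Under Regular Follow-ups, protocol section 7.3 fixes an order for the visit: "Prior to completing the required assessments, the subject will have his/her stimulator reprogrammed if needed". The sentence covers the required assessments as a whole. No visible text makes an exception for the VAS, sets a minimum time between reprogramming and scoring, or asks for a record of which scores followed a reprogramming.

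The VAS carries the primary objective. Section 2 gives two summaries: "The average pain reduction experienced as well as the percentage of subjects with at least a 50% pain reduction will be evaluated". For baseline, section 7.3 describes the method: "Baseline pain scores (VAS) will be evaluated using the average score from a 4 day pain diary completed by subjects before their trial procedure". The text at hand gives no corresponding diary, recall period or number of readings for follow-up. Section 7.1 refers to Table 1 in Appendix A for the assessments at each visit, and section 7.3 says of the CRFs: "A copy of the CRFs will be provided for review". Neither is in the supplied text.

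Settings can also change between visits. Section 7.3 says "Each subject will receive a hand-held Patient Programmer that can be used to adjust stimulation amplitude as needed throughout the study duration", and, on interim visits, "subjects will have the option to return to the study site at any time to have their neurostimulator re-programmed to achieve maximal benefit".

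**The concern.** Section 1.4 gives the purpose as long-term prospective data on how the system performs in routine patients. A current-pain score taken just after an adjustment describes the new settings. It does not describe relief under the settings the subject arrived with. If the adjustment was made because relief had faded, that loss of relief is what a long-term study should record, and the stated order may remove it from the primary score.

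Nothing else in the design offsets this. Section 7.2 confirms that there is one arm and no blinding, so no control group undergoes the same visit sequence, and the outcome is self-reported. A subject who knows that the device has just been adjusted may also score with that in mind. Baseline averages several days, so a single score after adjustment would not be measured in the same way as the value it is compared with.

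This is a matter of data collection. If no score is taken before reprogramming, no later analysis can recover it.

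**Working it through.** The protocol states no figure on this point, so there is none to reproduce. The check sets the passages side by side and then shows what the order could do under stated assumptions.

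**Who could be affected.** Only subjects reprogrammed at a scheduled visit, and only for that visit's score.

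| Follow-up VAS asks about | Effect of the stated order |
|---|---|
| Days before the visit (diary or recall) | About zero, because the score refers to time before the change |
| Current pain | Score refers to settings changed at that visit |

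The visible text does not say which row applies.

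**Figure from the document.** The Summary gives the planned enrolment: "Up to 125 Males and females at least 18 years of age". One reclassified subject moves the responder share by 100 × 1/125 = 0.8 points. This is a minimum, because no more than 125 can be analysed. With an assumed 100 or 80 analysed it is 1.0 or 1.25 points.

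**Worked example (invented subject).** Take a baseline of 60 mm, which is the eligibility figure in section 4.2 and not a mean. The 50% threshold is 60 × 0.5 = 30 mm. A subject living with 40 mm has a reduction of (60 − 40)/60 = 33% and is a non-responder. If the same subject reports 30 mm after adjustment, the reduction is 50% and the subject counts as a responder.

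**Assumed range for a current-pain VAS.** Let p be the share reprogrammed at a visit, δ the mean change in their score (negative means less pain), a the share of them who become responders and b the share who cease to be. All values are assumptions: p = 10% to 30%, δ = −20 to +5 mm, a = 0 to 40%, b = 0 to 10%.

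- Shift in the overall mean VAS = p × δ. Lowest: 0.30 × (−20) = −6.0 mm. Highest: 0.30 × 5 = +1.5 mm.
- Shift in the responder share = 100 × p × (a − b). Lowest: 100 × 0.30 × (0 − 0.10) = −3 points. Highest: 100 × 0.30 × (0.40 − 0) = +12 points.

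The ends combine the most extreme inputs, and the lean towards the device is built into the assumed ranges.

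**Second illustration, also assumed throughout.** Take a baseline of 75 mm and follow-up scores that are normal with mean 37.5 mm and SD 25 mm, so that 50% respond. If a share f is reprogrammed and their scores fall by d mm, the mean falls by f × d and the responder share rises by 100 × f × [Φ(d/25) − 0.5] points.

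| f | d (mm) | Fall in mean (mm) | Rise in responders (points) |
|---|---|---|---|
| 10% | 5 | 0.5 | 0.8 |
| 30% | 10 | 3.0 | 4.7 |
| 50% | 20 | 10.0 | 14.4 |

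With a pre-visit recall period, δ, d, a and b are all zero, and so is every shift above.

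**The case against.** The strongest reply is that the deciding fact lies in text that is not supplied. Appendix A and the CRFs may set a recall period or a diary for follow-up, and the only VAS method that the visible text describes is a multi-day average. If follow-up uses the same method, the order hardly matters. This stands, and it makes the point conditional. It does not remove it, because section 7.3 itself fixes the order and makes no exception.

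A second reply is that the order may be deliberate. The protocol treats programming as part of the therapy, and pain under optimised settings is a legitimate target. No visible text names that target, however, and a second score after reprogramming would serve it without losing the first.

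Third, a single score on arrival is not a clean remedy either. It captures one moment, it does not measure pain since the last visit, and subjects can alter amplitude themselves beforehand. This also stands. An arrival score corrects the order but not the mismatch with the diary baseline; a pre-visit diary corrects both.

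Interim visits and the patient programmer limit the effect, since some lost relief will be dealt with before a scheduled visit. The optional telephone contacts should not be counted in the same way. The protocol says only: "If desired, the Investigators may call the subjects for evaluation at 8-weeks, 9-months and 18 months post-implant". It does not say that they lead to reprogramming.

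Finally, the direction is not assured. An adjustment for poor relief should lower the score, but one made for comfort could raise it.

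**Conclusion.** The point holds in conditional form and should be fixed, with medium confidence. The order is explicit, and no visible text exempts the primary VAS. If the follow-up VAS asks about current pain, the scores of subjects reprogrammed at that visit can misstate relief under the settings they had been living with. The effect is probably in favour of the device.

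Its size is unknown. Apart from the minimum of 0.8 points per reclassified subject, every shift shown rests on assumed inputs, because the protocol does not say how many subjects are reprogrammed or how their pain changes afterwards. Under a pre-visit diary or recall period the effect is about zero.

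A reader might infer that the protocol never collects a VAS before reprogramming, or that the primary result is biased. The documents support neither reading: the per-visit table and the CRFs are not shown, and nothing visible establishes that the follow-up VAS asks about current pain.

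**What to change.** Amend the sentence in section 7.3 so that the follow-up VAS is obtained before any programming change at the visit. The preferred source is a short pre-visit diary that matches the 4-day baseline method; otherwise the VAS is completed on arrival. State the recall period, record whether reprogramming took place at the visit (if the CRF does not already do so), and use the pre-reprogramming value for both primary summaries. If pain under optimised settings is also of interest, collect a second VAS after reprogramming and report it separately. If Appendix A or the CRFs already set a pre-visit diary or recall period, a sentence in section 7.3 saying so is enough.

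Whether and how the device is reprogrammed does not change. The cost is a small edit to section 7.3 and at most one yes/no CRF field, with no extra visit. Reprogramming would start a few minutes later if the VAS is completed on arrival, a diary adds a small burden for subjects, and reported relief may look slightly less favourable.

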**7.4 Withdrawal of individual subjects**

Subjects can leave the trial at any time for any reason without any consequences. The investigator can decide to withdraw a subject from the trial for urgent medical reasons.

**7.5 Replacement of individual subjects after withdrawal**

Subjects that are withdrawn during the trial will not be replaced.

**7.6 Follow-up of subjects withdrawn from treatment**

Subjects will continue to receive normal, standard clinical care by the study physician.

**7.7 Premature termination of the study**

The Prospective Trial will be terminated prematurely if the Investigators or REC feel there is a risk to the subjects enrolled. Subject safety will continue to be monitored by the Investigators for the duration of the device.

## 8. SAFETY REPORTING

### 8.1 Applicable laws and regulations

For the reporting of events in this study, we will follow applicable international standards and guidance documents for CE marked products (AIMDD, MEDDEV 2.12/2 rev2 and MEDDEV 2.12-1 rev 8), the applicable local laws and regulations, and the SMI internal operating procedures on complaint reporting (OP #058), whichever is the most stringent.

In this regard we will only report device related AE/SAEs and any unanticipated SAE's.

Additionally, all reported events will be reviewed internally at Spinal Modulation Inc. according to the criteria for incidents to be reported by manufacturers to competent authorities, as defined in section 5.1.1 in the MEDDDEV 2.12-1 Rev 8.

### 8.2 Definitions

We will use the ISO14155:2011 as reference for the definitions of events.

#### *Adverse Event (AE):*

Any untoward medical occurrence, unintended disease or injury, or untoward clinical signs (including abnormal laboratory findings) in subjects, users or persons, whether or not related to the investigational device.

#### *Serious Adverse Event (SAE):*

Any AE that led to:

- death
- serious deterioration in the health of the subject, that either resulted in
  - a life threatening illness or injury, or
  - a permanent impairment of a body structure or body function, or
  - in-patient or prolonged hospitalisation, or
  - medical or surgical intervention to prevent life-threatening illness or injury or permanent impairment to a body structure or body function
- foetal distress, foetal death or a congenital abnormality or birth defect

Planned hospitalization for a pre-existing condition, prolonged hospitalization as a result of a revision procedure, which is allowed in the protocol or a procedure required by the protocol, without serious deterioration in health, is not considered a serious adverse event.

*Unanticipated:*

An event which by nature, incidence, severity or outcome has not been identified in section 6.2 of this protocol.

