## 6.2 Summary of known and potential risks and benefits

A summary of the known and potential risks and benefits can be found in the accompanying manuals that are included in the package of the components. The general risks associated with the Axium® Neurostimulator System are similar to those associated with other currently approved Spinal Cord Stimulator systems. Possible risks to the subjects include both device and procedural based risks. The most common side effects and risks are:

- Pain (where the needle is to be inserted)
- Pain caused by understimulation due to lead migration
- Pain over the implantable neurostimulator site (only applicable in Phase 2)
- Escalating pain
- Bleeding (where the needle has been inserted)
- Headache
- Infection
- Localized collection of serous (clear) fluid at injection site
- Discomfort during the treatment
- Allergic or rejection response to implant materials
- Constant pain at the lead site
- Stimulation of the chest wall
- Lead migration (movement) and/or local skin breakage
- Weakness
- Clumsiness
- Numbness
- Temporary muscle activation

Very rare risks and side effects include:

- Cerebral Spinal Fluid (CSF) leakage
- Tissue damage
- Nerve damage
- Spinal cord compression
- Paralysis
- Hematoma
- Seroma
- Sensory loss
- Skin erosion around the INS or leads
- Battery failure and/or battery leakage
- Lead breakage requiring replacement of the lead
- Hardware malfunction requiring replacement of the neurostimulator
- Pain from a non-injurious stimulus to the skin (allodynia)
- An exaggerated sense of pain (hyperesthesia)

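### The SAE definition exempts hospital stays prolonged by a revision, so unplanned re-operations caused by the device can be classed as non-serious

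*Protocol*

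**What the plan says.** Section 8.2 defines an SAE as an AE that led to death, to a foetal or congenital outcome, or to "serious deterioration in the health of the subject, that either resulted in" one of four listed results. One of these is hospitalisation: "in-patient or prolonged hospitalisation, or". Another is "medical or surgical intervention to prevent life-threatening illness or injury or permanent impairment to a body structure or body function".

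A closing sentence then sets three things outside the definition: planned hospitalisation for a pre-existing condition, and "prolonged hospitalization as a result of a revision procedure, which is allowed in the protocol or a procedure required by the protocol". It ends with a proviso: "without serious deterioration in health, is not considered a serious adverse event".

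The other relevant places are:

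- **Section 7.3**, under the item on interim programming, revision, replacement and explant, provides for these where necessary, when part of the system stops working or needs adjusting. It sets no limit on the cause of a revision.
- **Section 6.2** lists lead migration among the most common risks. Among the very rare risks it lists "Lead breakage requiring replacement of the lead" and hardware malfunction that requires a new neurostimulator.
- **Section 8.1** sets the reporting scope: "we will only report device related AE/SAEs and any unanticipated SAE's".
- **Section 8.3** has the sponsor forward reported SAEs to the Chief Investigator. It names no such step for non-serious AEs.
- **The Summary** gives the secondary objectives as "Safety (AE/SAE), Quality of life, Physical functioning, Subject satisfaction and Device performance".

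**The concern.** Two of the three exempted items are foreseeable and say nothing about harm from the device: an admission already planned for another condition, and a stay for a procedure that the protocol itself requires. Revision is different. It usually answers a complication of the device, such as a lead that has moved. The words limiting the exemption to revisions that the protocol allows filter nothing, because section 7.3 excludes no revision.

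Safety, recorded as AEs and SAEs, is a secondary objective of this 24-month post-market trial. If a re-operation for a device complication keeps a patient in hospital longer and is then recorded as non-serious, the SAE count is lower than a reader would expect. Sites that read the sentence differently will also classify the same event differently.

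**Working it through.** The plan states no SAE rate or revision rate, so there is no figure to reproduce. The check is a reading of the text, followed by one illustration of scale.

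**Step 1. What the exemption covers.** It names prolonged hospitalisation after a revision. It does not name new in-patient admission, although the SAE list has both in-patient and prolonged hospitalisation. Section 7.3 lists replacement and explant beside revision, and the exemption names neither. It also leaves the intervention criterion untouched. Within that narrower scope, it covers revisions of any cause.

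**Step 2. What the proviso does.** Set beside the SAE list, it can be read in three ways:

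- *Hospitalisation as a marker of serious deterioration.* A prolonged stay then shows serious deterioration, the proviso is never met, and the exemption is empty.
- *Serious deterioration judged separately from the stay.* A stay without it would not meet the SAE criteria in any case, and the exemption is redundant.
- *The proviso attached only to the last item, procedures required by the protocol.* The revision exemption then has no condition. The commas permit this, though it is not the natural reading.

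The exemption changes a classification under the third reading. It also does so when a site mixes the first two, taking hospitalisation as sufficient in the list but judging deterioration clinically in the exemption. The protocol gives no test that prevents either.

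**Step 3. What follows from losing SAE status.**

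| Attribution of the prolonged stay | If an SAE | If exempted |
|---|---|---|
| Device-related | Reportable (8.1); forwarded to the Chief Investigator (8.3) | Reportable as a device-related AE (8.1); no forwarding step stated |
| Procedure-related only, unanticipated | Reportable as an unanticipated SAE (8.1) | Not within the stated scope of 8.1 |
| Procedure-related only, anticipated | Not within the stated scope of 8.1 | Not within the stated scope of 8.1 |

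The exemption therefore matters in the first two rows. The table assumes that a site may treat device-related and procedure-related as separate categories; the visible text does not define the boundary.

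**Step 4. Scale.** Inputs: the enrolment maximum N = 125 (Summary), and an assumed number r of subjects whose only potential SAE is an exempted stay. The reduction in the SAE proportion is r / N.

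- r = 1: 1/125 = 0.8 points
- r = 5: 5/125 = 4.0 points
- r = 10: 10/125 = 8.0 points
- r = 15: 15/125 = 12.0 points

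The documents give no basis for choosing r. If fewer than 125 subjects are implanted and they form the denominator, each such subject weighs more than 0.8 points.

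**The case against.** The strongest reply is that the proviso already protects serious events. On the natural reading, a revision with serious deterioration stays an SAE. Apart from death and foetal or congenital outcomes, the definition requires serious deterioration anyway, so a stay without it would not clearly qualify even if the exemption were deleted. This stands in part: events with clear serious deterioration are not removed. It does not rescue the sentence, because on that reading the revision clause has no function, and on the others it lowers the count.

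A second reply is that events are reclassified and not lost. Device-related AEs remain reportable under 8.1, where reported events are also reviewed against manufacturer incident criteria. Section 8.4 follows reported events until they resolve or stabilise, and an independent safety officer evaluates AE and SAE data (8.5). Section 7.3 refers to assessments for a revision, and device performance is a separate objective. This stands for device-related events. It does not fully stand for stays attributed to the procedure alone (second row of the table). Section 8.1 also defers to the most stringent of several external rules, which might bring some of these back, but their content cannot be checked here.

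A reader might also infer that every re-operation for device failure drops out of both the SAE and the unanticipated categories. The documents do not support that. New admissions, replacements and explants are not named in the exemption. Nor does a complication's appearance in 6.2 settle whether it is anticipated: the 8.2 definition also looks at how often it occurs, how severe it is and how it ends. Lead breakage and hardware malfunction are listed as very rare, so a higher frequency could make them unanticipated.

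**Conclusion.** The concern holds in a limited form. The revision clause reaches unplanned re-operations for device complications, and its proviso is partly circular and unclear in scope. Prolonged stays after such revisions can therefore be classed as non-serious, and the SAE count can understate serious device-related harm.

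The size cannot be estimated from the documents. The 0.8 points per affected subject is arithmetic on the enrolment maximum, not a forecast. A reader might assume other SAEs in 2–5% of implanted subjects and revision stays in 5–15%, and infer a true rate of 7–20% (2 + 5 to 5 + 15). Both inputs would be invented, and the sum assumes no overlap and that every such stay would otherwise be an SAE.

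It also does not follow that a main serious outcome of the device is removed from a reported SAE rate. The visible text defines no SAE-rate endpoint, the analysis sections are redacted, and the events listed in step 1 as outside the exemption are unaffected. Whether the sentence departs from the ISO standard cited in 8.2 cannot be judged from the documents.

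**What to change.** Reword the closing sentence of the SAE definition in section 8.2:

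- Limit the exemption to planned hospitalisation for a pre-existing condition and to the planned TNS and INS procedures.
- Delete the revision clause, so that an unplanned revision with in-patient or prolonged hospitalisation is assessed under the ordinary SAE criteria.
- State that the proviso on serious deterioration applies to each exempted item.

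The cost is one reworded sentence, a few more SAE forms and a somewhat higher reported SAE count. If the change counts as a substantial amendment, section 11.2 requires notice to the ethics committee. Patient treatment and the visit schedule are unaffected. A separate table of revisions and related hospital stays would help readers, but it belongs to the analysis plan, and its absence from the protocol is not part of this point.
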